Thus, this study will provide essential data on two techniques to help decipher which is the optimal method of tissue acquisition.

We hypothesize that the SINK technique will have a higher diagnostic accuracy than EUS-CNB for the diagnosis of UGI SETs.

4. Study Procedures

- Study design, including the sequence and timing of study procedures (distinguish research procedures from those that are part of routine care).

This is a prospective, randomized study. All procedures are part of routine care and not experimental. All patients will begin their endoscopy with a standard gastroscope followed by electronic radial/linear scanning video echoendoscope prior to randomization to ascertain the wall layer of origin for the tumor. This EUS exam will be performed under the same anesthetic as the study intervention. Patients will be consented prior to endoscopy.

Patients who are candidates for this study (see inclusion criteria) will be randomized as to receive either EUS-CNB or SINK technique (computer generated randomization sequence, sealed envelopes). The endoscopist will not be blinded to the type of technique used however the study pathologist will be blinded.

Patients receiving the EUS-CNB technique:

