Linear EUS will be used with color and pulsed Doppler to scan the area for vessels. The accessory channel is used to pass through devices for tissue sampling. The lesion will be sampled with a 22-gauge Procore needle (ProCore, Cook Medical Inc., Winston-Salem, NC) using the slow capillary suction technique with 5 to 15 to-and-fro movements with each pass. The slow capillary suction technique and fanning techniques will be used with each pass. The slow capillary suction technique involves the assistant simultaneously pulling out the stylet slowly and continuously over approximately 20s while the stylet is simultaneously removed up to 2/3 of its entire length. The fanning technique will be used. This technique involves positioning the needle at 3 different areas within the mass and then moving it back and forth 5 times in each area to procure tissue (3×5). The needle will be positioned at different areas within the mass by using the “up-down” dial of the echoendoscope and with minimal use of the elevator to avoid needle dysfunction. A total of 4 passes will be performed and then the procedure terminated. No cytopathologist will be present to review the specimens. All specimens will be placed in formalin bottles and sent for histopathology. If the samples are of insufficient quality such that a histological diagnosis would not likely be obtained after a total of 4 passes as per the impression of the endoscopist, he/she will be permitted to perform an alternative method; such as, SINK, EUS-FNA, EUS-CNB etc...

Definitions:

Technical Failure: Inability to complete the 4 assigned passes as determined by randomization. Malfunction of the needle before 4 needle passes is an example.

Adverse events: Refer to Tables 1 and 2. [12]

Operation Time: Time from the beginning of the incision or needle insertion, to completion of tissue acquisition per protocol.

Patients receiving the EUS-SINK technique:

A conventional needle-knife sphincterotome (Microknife XL; Boston Scientific Inc, Natick, Mass) connected to an electrosurgical unit (ICC 200; ERBE Electromedizin, Tübingen, Germany) will be utilized. The setting used would be ENDOCUT I, Effect 3, Duration 2 and Interval 1. Under direct endoscopic vision, a 6 to 12-mm linear incision is made from the periphery of the lesion to the highest convexity zone of the lesion. This direction of cut is important as it will help avoid unnecessary extension of the incision outside the lesion from

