slipping of the knife off the lesion. The incision should be deep enough such that it penetrates the mucosa and submucosa. A conventional biopsy forceps (Radial Jaw4, Boston Scientific, Natick, Mass) is then deeply introduced through the hole, and 2 bites are obtained per pass. A total of 4 passes will be performed, by passing the biopsy forceps through the incision on each occasion. The mucosal incision will then be closed with endoclips whenever possible. If the endoscopist at the time is concerned about inadequate tissue acquisition and plans to perform a subsequent intervention (i.e. EUS-CNB, EUS-FNA) then the endoclips will be placed after the EUS. Biopsies will be placed in formalin bottles and sent for histopathology. In case of technical failure, the endoscopist is permitted to choose another method to obtain biopsies (e.g. EUS-CNB, EUS-FNA...)

Pathologic evaluation

Specimens will be placed in buffered formalin and processed as normal forceps biopsy specimens; however, special care will be taken not to lose tiny specimen fragments. The pathologists will be blinded to the type of technique used, but all other information about the clinical history and site biopsied will be given. A positive diagnosis of a specific malignancy or of a specific benign disease by either technique will be accepted as a true positive. A histological diagnosis of atypical cells or abnormal cells will be considered a negative result. For malignancy, an “accurate diagnosis” will be considered one in which a tissue diagnosis obtained is compatible with that seen by subsequent surgery, alternative biopsy by another needle or sites, or clinical follow up.

Final diagnosis and definition

In the absence of surgical resection, diagnostic histology obtained by either technique will be considered the gold standard. When diagnostic histology is not available, a definitive diagnosis is established on the basis of long-term follow-up, surgery, or further procedures with biopsy. The diagnostic accuracy will be defined as the ratio between the sum of true positive and true negative values divided by the total number of procedures done in either technique. As per the discretion of the pathologist, the specimens may be subjected to immunostaining and if performed, the contribution to the diagnostic yield will be noted.

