The study will be continued until the sample size of 90 patients is reached (estimated 2 years). The patients will only need to attend for the procedure as scheduled. No further visits are required.

b. Blinding, including justification for blinding or not blinding the trial, if applicable.

Blinding of the endoscopist is not practical as the endoscopist will be performing the technique. However, the pathologist will be blinded to the technique used.

c. Justification of why participants will not receive routine care or will have current therapy stopped.

Not applicable. This study compares two techniques which are considered standard of care for the diagnosis of these tumors. These procedures are not experimental.

d. Justification for inclusion of a placebo or non-treatment group.

This is not applicable to this study. All patients are presenting for a procedure they require for diagnosis as determined by their referring physician.

e. Definition of treatment failure or participant removal criteria.

In case of failure of the initial method to obtain adequate sample, another method may be performed at the discretion of the endoscopists. An inadequate sample is defined as samples of insufficient quality such that a histological diagnosis would not likely be obtained. This will be determined at the time of tissue acquisition if the samples obtained are only tiny fragments, no visible core tissue (i.e no worms) or it appears that only blood clot is present. Post procedure, an inadequate sample will be determined based on an inconclusive formal pathology report. In these cases, the patients may cross over to EUS-CNB or SINK (depending on their initial randomization) or undergo an EUS-FNA either at the time of the procedure (if it appears that no tissue has been obtained) or the patient will return at a later date for an EUS-CNB, SINK, EUS-FNA/be referred to surgery/undergo surveillance at 6-12 months etc, depending on the differential diagnosis.

f. Description of what happens to participants receiving therapy when study ends or if a participant's participation in the study ends prematurely.

This is not applicable in this study. The patient only attends for their diagnostic procedure; there is no further follow-up or treatment necessary as part of the study protocol.

5. Inclusion/Exclusion Criteria

Inclusion criteria:

1. Patients referred for EUS evaluation of upper GI SETs measuring an estimated 15mm or greater in maximal diameter.

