2. Location of SET: esophagus, stomach, duodenum
3. Age >18 years and older
4. Patient consent obtained

Exclusion Criteria:

1. Endoscopically non bulging lesion
2. Upper GI SETs <15mm in size as measured during study EUS
3. Lesions not necessitating tissue acquisition: i.e. lipomas, varices
4. Cystic lesion
5. Patients < 18 years of age
6. Uncorrectable Coagulopathy (INR >1,5, platelets <100,000)
7. Patients with stigmata of portal hypertension
8. Patients with post-surgical UGI anatomy (Roux-en-Y gastric bypass, esophagectomy etc)
9. Uncooperative patients
10. Pregnant women (women of childbearing age will undergo urine pregnancy testing, which is routine for all endoscopic procedures)
11. Refusal to consent form

Drop-outs (anyone will be considered a drop-out after randomization had been made):

1. Mass<15mm
2. Cystic
3. Lipoma
4. Varices

6. Drugs/ Substances/ Devices

- a. The rationale for choosing the drug and dose or for choosing the device to be used.

The 25 G needle is too small to be used for histological sampling, and the 19 G needle is too rigid impeding the sampling from the duodenum or the fundus of the stomach. The 22G Procore needle is readily available and clinically used for tissue sampling.

The needle knife sphincterotome and pinch biopsy forceps are readily available and used clinically for controlled mucosal incision and tissue sampling allowing, respectively.

Although used clinically, neither of these techniques has been compared at our institution.

- b. Justification and safety information if FDA approved drugs will be administered for non-FDA approved indications or if doses or routes of administration or participant populations are changed.

Not applicable

- c. Justification and safety information if non-FDA approved drugs without an IND will be administered.

Not applicable

7. **Study Statistics**

- a. Primary outcome variable.

We hypothesize that the diagnostic accuracy of single incision using needle knife (SINK) technique will “be superior” in obtaining histological samples than EUS-CNB.

Based on the previously published references that demonstrated the diagnostic accuracy of SINK is 92.8%⁸ and that of EUS-CNB is 70% [12], we assume that the diagnostic accuracy of SINK and EUS-CNB to be 95% and 70% respectively

- b. Secondary outcome variables.
 - Not applicable
- c. Statistical plan including sample size justification and interim analysis

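### Four exclusion conditions also serve as post-randomisation drop-outs, with no tie to data recorded before allocation and no stated analysis set

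*Combined protocol and SAP*

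**What the plan says.** Section 5 (Exclusion Criteria) excludes lesions measured under 15 mm at the study EUS, lesions that need no tissue such as lipomas and varices, and cystic lesions. A separate drop-out list in the same section repeats these four conditions and says that "anyone will be considered a drop-out after randomization had been made".

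Section 4a has every patient examined with a gastroscope and then an "echoendoscope prior to randomization to ascertain the wall layer of origin for the tumor". Wall layer is the only purpose given for that examination. Section 4b states that "Blinding of the endoscopist is not practical as the endoscopist will be performing the technique"; only the pathologist is masked.

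Under Pathologic evaluation, "A positive diagnosis of a specific malignancy or of a specific benign disease by either technique will be accepted as a true positive". Under Final diagnosis and definition, accuracy is true positives plus true negatives, "divided by the total number of procedures done in either technique". Section 7c needs 72 patients and enrols 90 to allow for 20% drop-out. No section names an analysis set, says who declares a drop-out, or says from what evidence.

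**The concern.** Leaving out patients who never met the entry criteria is acceptable when the judgement rests on facts fixed before allocation, because allocation cannot then influence who is removed. Here that safeguard is not written. The size exclusion is tied to the study EUS, but the drop-out list carries no such tie, and cystic lesion, lipoma and varices have no stated source of evidence in either list. The person best placed to declare a drop-out during the procedure knows the arm.

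Lipoma raises a second difficulty. If it is recognised on imaging and the lesion is not sampled, nothing conflicts. If it is first found in the study biopsy, the sample has succeeded and counts as a true positive, yet the drop-out list would remove that patient. Removal would then depend on the primary outcome.

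At stake is whether the patients compared on diagnostic accuracy are still the groups that were randomised, and whether the denominator is fixed before results are known.

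**Working it through.** **Inputs from the documents.** Assumed accuracy 95% (SINK) and 70% (EUS-CNB), section 7a. Alpha 5%, power 80%, 36 per arm, 20% drop-out, 45 per arm, section 7c. Sidedness is not stated; two-sided is assumed here. The documents give no share for any of the four conditions, so every share below is an assumption.

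**1. The plan's own figures.** With pooled proportion 0.825, the two-sided normal approximation without continuity correction is

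n = [1.960·√(2·0.825·0.175) + 0.842·√(0.95·0.05 + 0.70·0.30)]² / 0.25² = 35.06, so 36 per arm.

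Then 72 / (1 − 0.20) = 90. Both figures reproduce. The allowance is 90 − 72 = 18 patients, or 9 per arm if even. Inflating in this way makes sense only if drop-outs leave the analysis, which is the sole basis for saying that they do. Power at 95% v 70% is 0.891 with 45 per arm and 0.811 with 36 per arm (Fisher's exact test: 0.863 and 0.759).

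**2. Lipoma removed on histology.** Let L be the lipoma share and p the accuracy, taken as the same in lipomas and other lesions. Correctly diagnosed lipomas (pL) are removed and missed ones stay, so

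observed accuracy = p(1 − L) / (1 − pL).

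| L | SINK | EUS-CNB | Difference (points) | Power |
|---|---|---|---|---|
| 0% | 95.00% | 70.00% | 25.0 | 0.891 |
| 1% | 94.95% | 69.79% | 25.2 | 0.890 |
| 2% | 94.90% | 69.57% | 25.3 | 0.890 |
| 5% | 94.75% | 68.91% | 25.8 | 0.889 |
| 10% | 94.48% | 67.74% | 26.7 | 0.887 |

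Power uses the expected numbers left, 45(1 − pL) per arm. If p is equal in the two arms, the formula gives the same value in both and the difference stays at zero.

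**3. Handling of unsampled patients.** Suppose both techniques are truly 82.5% accurate, and 10% of EUS-CNB patients only are left unsampled after late recognition, with SINK accuracy 82.5% in such lesions too. EUS-CNB accuracy is then:
- excluded: 82.5%, difference 0;
- counted as failures: 0.90 × 82.5% = 74.25%, a spurious 8.25 points in favour of SINK;
- counted as successes: 74.25% + 10% = 84.25%, a spurious 1.75 points against SINK.

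No single convention is safe by itself. The choice also affects power. If 20% in each arm were affected, excluding them leaves 0.811. Counting them as failures gives 0.80 × 95% = 76% v 0.80 × 70% = 56%, with power 0.517.

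**The case against.** The strongest reply is that the list means only ineligibility noticed late on imaging. EUS comes before randomisation, only candidates for the study are randomised, and size is measured at the study EUS. The accuracy denominator counts procedures done, so an unsampled patient is out and a sampled patient is in. On that reading there is no conflict with the definition of a true positive, and the denominator is largely settled. This is a natural reading, but the list does not state it, and it still leaves late removal open to someone who knows the arm.

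A reader might infer that late recognition must differ by arm. The EUS-CNB procedure says "Linear EUS will be used with color and pulsed Doppler to scan the area for vessels", while for SINK "Under direct endoscopic vision, a 6 to 12-mm linear incision is made". If ineligible lesions were removed in EUS-CNB only, made up 10% of lesions, and SINK accuracy in them were 0%, the planned difference would fall to 0.90 × 95% − 70% = 15.5 points. The documents do not support that as an estimate. The bleeding item in section 8a can be read as requiring Doppler under EUS before biopsy in both arms, although it speaks of a needle and does not fix the time relative to allocation. The EUS-CNB scan is aimed at vessels, not at re-measuring or reclassifying the lesion. None of the three assumptions has a source, and equal recognition gives no shift.

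A reader might also infer that removing failures from one arm would inflate the false-positive rate. It would, but that presumes selective removal, and nothing in the documents suggests it.

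**Conclusion.** The gap is real: a rule allows removal after allocation, by someone who may know the arm, for conditions that an existing examination could settle beforehand. That drop-outs leave the analysis is inferred from the 72-to-90 inflation, not stated. The size of any bias cannot be estimated from the documents. The one outcome-dependent route that can be worked through, lipoma on histology, moves the planned difference by 0.2 to 1.7 points at assumed shares of 1% to 10%, leaves power near 89% (two-sided normal approximation), and has no effect at equal accuracy. Recognition that differs by arm is a possibility, not a finding. The change is worth making because it closes a route to bias at very little cost, not because a large distortion has been shown.

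**What to change.** 1. Before the envelope is opened, record from the existing pre-randomisation EUS that the lesion is at least 15 mm and is not cystic, a lipoma or a varix. Do not randomise patients who fail this check.
2. Replace the drop-out list with one rule, applied identically in both arms: a randomised patient leaves the primary analysis only if the EUS record made before allocation shows one of the four conditions. Otherwise every patient in whom sampling has begun stays in the assigned arm. The existing start point for operation time, "Time from the beginning of the incision or needle insertion", can define when sampling begins. Histological lipoma counts as a specific benign diagnosis, and a non-diagnostic sample counts as a failure.
3. Report by arm, with reasons, any patient left unsampled because a condition was recognised only after allocation. Show the primary comparison with these patients excluded, counted as failures and counted as successes, and say in advance which version carries the test.
4. State that the accuracy denominator under Final diagnosis and definition follows this rule.

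The cost is one checklist line and one small table, with no extra procedure. A few ineligible lesions may stay in the analysis. The rule cannot prevent late recognition from differing by arm, but the by-arm report and the three versions would show how far the result depends on it.

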Subepithelial lesions of the upper gastrointestinal tract are frequently detected incidentally during upper endoscopy, with a prevalence of 0.36% [1]. The imaging modalities currently utilized are unable to accurately distinguish between the different types: lipoma, pancreatic rest, spindle cell tumor, fibroma, neuroendocrine tumor, hamartoma, hemangioma, and others. Karaca et al. reported a series of 22 patients with gastric subepithelial lesions that underwent a diagnostic EUS [9]. The accuracy based on sonographic imaging alone was 45.5% (10/22). There are multiple modalities to sample these lesions, including EUS-guided FNA, EUS-guided CNB, bite-on-bite forceps biopsies, mucosal incision with a fixed flexible snare, EUS-Trucut core biopsy (TCB), EUS-guided SINK and endoscopic resection.

EUS-FNA has been reported in the literature to be the current standard of care; however, it lacks sensitivity as the diagnostic yield was as low as 38% [8]. Another study by Sepe et al. revealed the sensitivity of EUS-FNA cytology for the diagnosis of GIST was 78.4% and was influenced by size, location, shape, and layer of origin [10]. Therefore, the

patient was often required to undergo further procedures to confirm the diagnosis. Thus a simple, safe, and more reliable technique is warranted for definitive diagnosis. DeWitt et al. demonstrated that a 19-gauge EUS-TCB provided diagnostic histology of 79% in 38 patients [11]. When including these 38 patients, these same authors summarized previous studies and found that the same needle yielded diagnostic histology in 74% of patients with mesenchymal GI tumors. Gwang et al. compared the 22G EUS-FNA technique with the 22G Procore needle (ECHO-HD-22-C, Cook Endoscopy, USA) on 28 patients revealing that the 22G biopsy group had a significantly lower median number of needle passes to obtain macroscopically optimal core samples (4 vs. 2, $p = 0.025$); higher yield rates of histologically optimal core samples with three needle passes (20% vs. 75%, $p = 0.010$, respectively); and a higher diagnostic sufficiency rate (20% vs. 75%, $p = 0.010$) [7].

[figure not shown]
The SINK technique has been described in a study involving 14 patients revealing a diagnostic yield of 92.8%, with no adverse events. Eight patients underwent both EUS-FNA and SINK, with final histologic diagnosis determined in 6 of 8 cases (75%) by SINK versus 1 of 8 cases (12.5%) by EUS-FNA (Fisher exact test, $P = 0.023$) [8].

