With the assumption that diagnostic yield of “EUS-CNB” is 70% and that of “SINK” is 95%, and considering $\alpha = 5\%$ and $1-\beta = 80\%$, the required sample size is 36 patients in each group (total of 72 patients).

We will account for 20% drop out rate, giving a total of 90 patients, 45 in each arm.

Statistical analyses

Categorical parameters including gender, location of lesion, technical success and diagnostic accuracy will be compared by χ^2 -test or Fisher’s exact test. To compare diagnostic accuracy between the two techniques, we will use McNemar’s test. Continuous variables including age, size of lesion, follow-up period, needle passes and adequacy of specimens will be compared by the Student’s *t*-test or Wilcoxon rank sum test. All statistical analyses will be performed using SPSS software (version 15.0; SPSS, Chicago, IL), with results considered significant at *P* values < 0.05 .

- d. Early stopping rules.

A data safety and monitoring board (DSMB) will be appointed comprised of interventional endoscopists, mainly of [name], [name], and [name]. The DSMB will be responsible for reviewing all major complications (perforation, hospitalization for > 48 hours, bleeding requiring transfusion, deaths etc). If any serious adverse event is noted during the study then the DSMB will be required to meet. Additionally. The DSMB will perform a blinded analysis after enrolment and initial outpatient follow-up of 50% of the study cohort.

Interim analysis will be performed at 50% recruitment. If a $> 20\%$ difference in sensitivity is found between both methods then the study will be terminated early.

8. Risks

- a. Medical risks, listing all procedures, their major and minor risks and expected frequency.

This study is classified as greater than minimal risk and potential complications related to EUS-CNB or SINK procedure are following:

- 1) The needle puncture may cause inflammation or scarring of the lining of the digestive tract which may cause abdominal pain and ulceration.
- 2) Perforation: Only physicians specially trained in EUS will be performing these procedures. Patients will be kept a minimum of 2 hours after the procedure is completed, during which time any perforation would be clinically recognized.

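### The primary accuracy comparison uses no baseline covariate although lesion size is already measured; this is valid, but one pre-specified size-stratified test could recover a little precision and settle which test is primary

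*Combined protocol and SAP*

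**What the plan says.** Diagnostic accuracy is the primary outcome (section 2). Section 7c, under Statistical analyses, deals with it twice. First, "Categorical parameters including gender, location of lesion, technical success and diagnostic accuracy will be compared by" a chi-square or Fisher's exact test. The next sentence assigns the comparison of accuracy between the techniques to McNemar's test. No regression model or stratified test appears anywhere.

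Lesion size enters the analysis only as a variable compared between arms: "Continuous variables including age, size of lesion, follow-up period, needle passes and adequacy of specimens will be compared by" a t-test or Wilcoxon test.

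Randomisation is described in section 4 as "computer generated randomization sequence, sealed envelopes", with no stratification factor. The same section places an EUS examination "prior to randomization to ascertain the wall layer of origin for the tumor". Section 5 excludes lesions under 15 mm as measured at the study EUS. It also lists a mass under 15 mm among the reasons for counting a patient as a drop-out after randomisation.

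On predictors of sampling success, section 3 (Background) cites one study of EUS-FNA cytology in which sensitivity for GIST "was 78.4% and was influenced by size, location, shape, and layer of origin".

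**The concern.** A baseline variable that predicts whether a biopsy succeeds adds noise to the comparison of two techniques when it is left out of the analysis. In a small trial it can also differ between arms by chance. Here one candidate, lesion size, is measured anyway, and the protocol's own background names it as an influence on a related technique. Comparing size between arms, as section 7c plans, does not adjust the accuracy estimate.

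What is at stake is some precision, not validity. The tests named for the primary outcome have to be revised in any case: McNemar's test is for paired observations, and the two arms here are independent patients. The covariate question can be settled in the same edit.

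**Working it through.** **1. The plan's own figure.** Section 7 assumes accuracies of 95% (SINK) and 70% (EUS-CNB), alpha 5% and power 80%. With a two-sided test and pooled variance, mean accuracy is (0.70 + 0.95)/2 = 0.825, and

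n = [1.960 × √(2 × 0.825 × 0.175) + 0.8416 × √(0.70 × 0.30 + 0.95 × 0.05)]² / 0.25² = (1.053 + 0.427)² / 0.0625 ≈ 35.1, rounded up to 36 per arm.

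Then 72/0.80 = 90. Both of the plan's figures reproduce, and nothing below changes them.

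**2. Is the unadjusted comparison valid?** Trials of 36 per arm were simulated with size as a continuous covariate and an assumed odds ratio for accuracy of 1 to 4 per SD of size. The unadjusted risk difference averaged 0.250 against a true 0.25. With both arms at 70%, the chi-square test rejected in 5.1-5.4% of trials. There is no systematic bias and no material excess of false positives.

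**3. How large is chance imbalance?** Suppose half the lesions are small (an assumption). The SD of the between-arm difference in their share is √(2 × 0.25/36) = 0.118, so the 95% range is ±1.96 × 0.118 = ±0.23. The ordinary sampling SD of the risk difference is √[(0.21 + 0.0475)/36] = 0.085, or 8.5 points. Under the strongest size effect tried, adjustment moves the estimate by an SD of about 3.1 points. That is noticeable, but well inside the sampling error that the unadjusted test already allows for.

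**4. What does stratifying gain?** The table gives simulated power at 36 per arm for the unadjusted chi-square test and the Cochran-Mantel-Haenszel (CMH) test without continuity correction. Half the lesions are small, and average accuracies stay at 70% and 95%. Every size effect is an assumption.

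| Accuracy, small/large lesions: CNB; SINK | Chi-square | CMH | Change (points) |
|---|---|---|---|
| 50/90; 90/100 (strong) | 85.2% | 88.4% | +3.2 |
| 55/85; 92/98 (moderate) | 85.3% | 86.2% | +0.9 |
| 60/80; 93/97 (weak) | 85.3% | 85.2% | -0.1 |
| 70/70; 95/95 (none) | 85.0% | 84.0% | -1.0 |

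Type I error of the CMH test was 5.0%. If only 20% of lesions are small (CNB 46/76, SINK 90/96), power is 85.2% against 84.9%, so there is no gain. The sample-size formula gives 81.1% at 36 per arm. It is an approximation with few failures, so the rows should be compared with each other and not with the planned 80%.

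**5. Does another model agree?** With size continuous and linear adjustment, the ratio of adjusted to unadjusted variance was 1.015, 0.99, 0.96, 0.91 and 0.86 at odds ratios of 1, 1.5, 2, 3 and 4 per SD. Power was 84%, 85%, 86%, 88% and 89%, against about 85% unadjusted. The pattern is the same: a slight loss if size is irrelevant, and a modest gain if it matters a good deal.

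**6. Why one binary factor and a Mantel-Haenszel method?** Expected failures are 36 × 0.30 + 36 × 0.05 = 12.6. The chance of no failure at all in the SINK arm is 0.95^36 = 0.158, and a logistic treatment effect then has no finite estimate. The Mantel-Haenszel risk difference remains defined. So few failures will not support several covariates.

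**7. Is size known before allocation?** Section 4 puts the EUS before randomisation, with wall layer as its stated purpose. The section 5 exclusion implies that size is measured at that examination. The section 5 drop-out list implies that a lesion may be found too small only after randomisation. The two statements must be reconciled before size can serve as a stratum.

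**The case against.** The strongest objection is that the documents give little ground for singling out size. The cited evidence concerns EUS-FNA cytology for one tumour type. It lists four factors without ranking them and gives no effect size. It says nothing of EUS-CNB or of SINK, which is an incision followed by forceps biopsy. Location and layer of origin have the same standing, and layer is the stated purpose of the pre-randomisation EUS. The gain could be nil or slightly negative, and no size distribution is given to support any particular cut. All of this stands, and it limits the point to a low-cost efficiency suggestion.

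A reader might go further and infer that size drives sampling success, so that the unadjusted difference is confounded by it. The documents do not support that. The word used is an influence, on another technique, and randomisation keeps the unadjusted estimate unbiased. Nor should much be made of an extreme case. Pairing the strongest assumed effect with an imbalance at the edge of its 95% range gives (0.40 + 0.10)/2 × 0.23 ≈ 0.058, about 6 of the planned 25 points. Neither the effect nor the half-and-half split comes from the protocol.

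What survives is that the covariate is already collected, that the loss if it proves irrelevant is about one power point, and that the primary test must be rewritten anyway.

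**Conclusion.** The point holds as a modest, optional improvement in precision. The planned comparison takes no account of any baseline variable. An unadjusted chi-square or Fisher test would be valid and unbiased, and the sample size of 36 per arm (90 in total) is not wrong on this account. Stratifying by size changes power by about -1 to +3 points at 36 per arm. The sign and size of the change rest on assumed associations, and on an assumed share of small lesions, that the documents do not give. The stronger inference, that the omission biases the result or undermines the trial, is not supported. The ambiguity over which test is primary, with a paired test named for independent arms, matters more and should be corrected first.

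**What to change.** In section 7c, replace the chi-square/Fisher and McNemar wording for the primary outcome with one analysis for independent arms: a Mantel-Haenszel risk difference with its confidence interval and a Cochran-Mantel-Haenszel test, stratified by one binary lesion-size factor. State that the test is run without continuity correction, because the figures above assume this. Conservatism can cost more than stratification gains: in the same simulations Fisher's test had about 76% power against 85% for chi-square.

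Define the factor from the EUS size recorded before the envelope is opened. The sponsor should choose and justify the cut, and fix it before any outcome data are seen, including those for the interim analysis. If the sponsor judges location or layer to be the better single factor, the same structure applies, but the figures above were worked for size. Keep the unadjusted chi-square or Fisher test, naming which, as a sensitivity analysis.

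In section 5, reconcile the exclusion of lesions under 15 mm at the study EUS with the listing of the same finding as a drop-out after randomisation, and state when size is recorded.

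The cost is SAP wording and a recorded time point for size, with no new patients or measurements. The downside is the choice of a cut in advance and a possible loss of about one power point if size has no effect. Stratified envelopes are optional and not needed for the gain. If they are used, block sizes should be concealed, because the endoscopist is not blinded and small blocks make allocations easier to predict.
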